Sample Size Calculation:	Sample size considerations were based on precision estimates and the ability to construct 95% confidence intervals around point estimates for pharmacodynamics endpoints with reasonable precision. Sample sizes as small as 9 patients per arm will allow for construction of 95% confidence intervals with half-widths as small as 0.77 standard deviation units. For other assessments, the study is not powered for analysis with inferential statistics. All data will be summarized using descriptive statistics only. Continuous data will be summarized with number of patients (n), mean, median, minimum, maximum, standard of deviation, coefficient of variation and or geometric mean. Categorical data will be summarized with number and proportion of patients.

Table of Contents

Sponsor Approval and Signature Page	2
Synopsis	3
List of Tables	14
List of Terms and Abbreviations	15
1 INTRODUCTION	17
1.1 COVID-19.....	17
1.2 Overview of CM4620	18
1.3 Pre-Clinical Development of CM4620	18
1.3.1 Pre-Clinical Safety and Toxicology Studies.....	18
1.3.2 Preclinical Efficacy Studies	19
1.4 Clinical Development of Auxora	19
1.4.1 Single Ascending Dose and Multiple Ascending Dose Studies	19
1.4.2 Open Label Study in Patients with Acute Pancreatitis with Accompanying SIRS and Hypoxemia (CM4620-201)	22
1.5 Pharmacodynamic and Pharmacokinetic Study in Patients with Acute Pancreatitis (CM4620-202)	24
1.6 Study in Severe Covid-19 Pneumonia (CM4620-204).....	24
1.7 Rationale for Current Study and Selected Doses	25
2 OBJECTIVES AND ENDPOINTS.....	26
2.1 Primary Objective	26
2.2 Secondary Objectives.....	26
2.3 Endpoints	26
3 INVESTIGATIONAL PLAN	27
3.1 Study Design.....	27
3.2 End of Study	28
3.3 Sponsor Termination of the Study	28
4 SELECTION OF PATIENTS	29
4.1 Inclusion Criteria	29
4.2 Exclusion Criteria	29
4.3 Re-Screening.....	30
5 TREATMENT OF PATIENTS	31
5.1 Overview.....	31
5.2 Discharge Criteria	31
5.3 Prohibited Medications	32

5.4	Compliance	32
6	PROCEDURES	33
6.1	Enrollment Procedures.....	33
6.2	Discontinuation and Withdrawal	33
7	STUDY DRUG MATERIALS AND MANAGEMENT	34
7.1	Auxora Product Description	34
7.2	Placebo Product Description.....	34
7.3	Auxora and Placebo Storage.....	34
7.4	Auxora and Placebo Preparation.....	34
7.5	Auxora and Placebo Administration.....	35
7.6	Packaging and Labeling.....	35
7.7	Accountability, Handling and Disposal	36
8	VISITS AND STUDY SPECIFIC ASSESSMENTS.....	37
8.1	Screening.....	37
8.2	Baseline Assessment.....	37

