3 INVESTIGATIONAL PLAN

3.1 Study Design

This will be a single-blind study where the patient will not know if they are receiving Auxora or Placebo. The first 4 patients will be enrolled in Cohort 1 and randomized 3:1 to Auxora or Placebo. If dose escalation occurs, the next 4 patients will be enrolled in Cohort 2 and randomized 3:1 to Auxora or Placebo. If dose escalation continues, the next 8 patients will be enrolled in Cohort 3 and randomized 3:1 to Auxora or Placebo. The decision to escalate dosing will be made by CalciMedica in consultation with the PI after the review of safety events in Cohorts 1 and 2.

Consultation between the PI and CalciMedica will occur if any patient receiving Auxora in Cohorts 1, 2 or 3 experiences one of the cardiac conduction events listed below during the 144 hours after the Start of the First Infusion of Study Drug (SFISD):

- QTcF interval of \geq 500 msec; or
- QTcF prolongation of \geq 60 msec as compared to baseline; or
- Mobitz Type II second degree atrioventricular (AV) block; or
- Third degree or high grade AV block; or
- Polymorphic Ventricular Tachycardia;

If one of the listed safety events occurs in a patient who is receiving Auxora in Cohort 1 but the event is not thought to be dose limiting, 4 additional patients will be enrolled in Cohort 1 and randomized 3:1 to Auxora versus Placebo for a total of 8 patients enrolled in the cohort, 6 randomized to Auxora and 2 to Placebo. The PI and CalciMedica will consult after all 8 patients are enrolled to determine if dose escalation to Cohort 2 will occur. If one of the listed safety events occurs in a patient who is receiving Auxora in Cohort 1 and the event is dose limiting, further dosing will not occur using the planned dose regimens but may occur using a regimen that provides lower total exposure of drug.

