8.2 Baseline Assessment

- Draw blood samples for laboratory monitoring
- Perform the BAL and obtain fluid for flow cytometry, single cell RNA sequencing, biomarker/chemokine panel, SARS-CoV-2 PCR
- Obtain blood for biomarkers/chemokines at the time of the BAL

These blood tests for laboratory monitoring may be performed on blood already drawn in the previous 12 hours prior to randomization or after randomization but prior to the start of the first infusion of study drug. After performing procedures, proceed to randomization.

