8.13.6 Blood Biomarkers and Chemokines

Cytokines and chemokines in serum and BAL fluid supernatant that will be analyzed using Milliplex Human Cytokine/Chemokine Panel II MAGNETIC Premixed 23 Plex Kit and HCP2MAG-62K-PX23 and Milliplex Human Cytokine/Chemokine MAGNETIC BEAD Premixed 41 Plex Kit, HCYTMAG-60K-PX41 (with exclusion of RANTES, PDGFA, PDGFB which require 100-times dilution of serum/BAL fluid). Both an unbiased analysis of the data using hierarchical clustering on z-score normalized cytokine/chemokine levels as well as direct

pairwise comparison of the cytokine/chemokine levels between predefined groups (Auxora vs placebo, split by specific time points) will be performed

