10 STATISTICAL METHODS

10.1 General Considerations

Sample size considerations were based on precision estimates and the ability to construct 95% confidence intervals around point estimates for pharmacodynamics endpoints with reasonable precision. Sample sizes as small as 9 patients per arm will allow for construction of 95% confidence intervals with half-widths as small as 0.77 standard deviation units.

For other assessments (flow cytometry analysis of BAL, single-cell RNA-sequencing analysis of immune cells in BAL, plasma and BAL fluid cytokines/chemokines), the study is not powered for analysis with inferential statistics.

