10.6 PD Analysis

Primary analyses will leverage descriptive statistics to summarize the change in combined proportions of CD4, CD8, and monocytes in BAL fluid by dose arm. Point estimates and corresponding 95% confidence intervals will be reported. We will explore ANCOVA models to compare the difference in post-dose proportions by arm, adjusting for pre-dose levels. Normality assumptions will be assessed and in the event of violation of assumptions, transformations or nonparametric approaches will be considered. Subsequent pairwise comparisons of each dose

arm to placebo arm will be assessed as appropriate. Similar methods will be employed for additional flow cytometry endpoints as described above.

Exploratory analyses may also consider unsupervised methods including hierarchical clustering to further identify and visualize patterns in flow cytometry data.

Activation of all immune cell types will be assessed using integrative analysis of single cell RNA sequencing on all subjects across all time points. After demultiplexing reads will be aligned to a hybrid genome containing human (GRCh38) and SARS-CoV-2 (NC_045512.2) reference genomes. Resulting cell-by-gene matrices from all samples will be normalized using sctransform algorithm and integrated using BBKNN or scVI/scANVI approach followed by Leiden clustering, identification of marker genes for each cluster and assigning cell type identity to clusters (for details see [Grant et al., 2021](#)). It will be assessed whether treatment with Auxora resulted in emergence of the new clusters/cell types/cell states and markers characterizing these newly emergent populations will be evaluated. For homologous cell types differential genes expression analysis will be performed between Auxora- and placebo-treated subjects, split by time-points. The impact of Auxora treatment on detection of SARS-CoV-2 positive and negative strand RNA in infected cells will also be assessed. Differential gene expression will be performed on per-cluster level (as implemented in Scanpy package) and using multilevel statistics (per-cluster and per subject level, to assess biological variability within the group, using averaged RNA expression and DESeq2 framework).

10.6.1 Mortality at Day 60 and Day 30

Mortality rate at Day 60 and Day 30 for each treatment group will be estimated by the Kaplan-Meier procedure.

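### The chemokine arm comparison names no pre-dose adjustment, the gene analysis does not say which level supports an arm statement, and the SAP omits the first and describes the second differently

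*Protocol*

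**What the plan says.** **Chemokines.** Protocol 8.13.6 plans clustering of z-scores and a direct "pairwise comparison of the cytokine/chemokine levels between predefined groups (Auxora vs placebo, split by specific time points) will be performed". No pre-dose covariate or change score is named. The pre-dose sample exists: Protocol 8.2 sends baseline BAL fluid to the chemokine panel and adds "Obtain blood for biomarkers/chemokines at the time of the BAL". For cell proportions, Protocol 10.6 does plan to use the pre-dose value: "We will explore ANCOVA models to compare the difference in post-dose proportions by arm, adjusting for pre-dose levels". It extends similar methods to the other flow-cytometry endpoints, and the SAP (Pharmacodynamic Analysis) says the same. Neither document extends them to chemokines.

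**Gene expression.** Protocol 10.6 plans an Auxora-versus-placebo comparison by time point at two levels. One is per cluster in Scanpy ("Differential gene expression will be performed on per-cluster level (as implemented in Scanpy package) and using multilevel statistics"). The other is multilevel: "per-cluster and per subject level, to assess biological variability within the group, using averaged RNA expression and DESeq2 framework".

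**SAP.** Its primary objective includes chemokine release, but no chemokine measure appears among its outcomes and no chemokine analysis among its analyses. Its single-cell text selects variable genes by a DESeq2 likelihood-ratio test and then applies K-means. It mentions neither Leiden clustering nor Scanpy, and gives no per-subject analysis or arm contrast. It defers to the protocol only for pharmacokinetics.

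**Inferential status.** The protocol synopsis says, after calling the other assessments unpowered, "All data will be summarized using descriptive statistics only". Protocol 10.1 says of a list ending in "plasma and BAL fluid cytokines/chemokines), the study is not powered for analysis with inferential statistics". SAP Power Considerations repeats that other assessments are unpowered, while SAP Level of significance sets a two-sided 0.05 for every analysis.

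**The concern.** Chemokine release is part of the primary objective in both documents, and Protocol 10.2 lists the single-cell analysis under the primary pharmacodynamic endpoint. Protocol 1.7 says the study is meant to find the dose from BAL markers. With 3:1 allocation the placebo group is small: 4 patients under the protocol's cohorts and 8 at the 32-patient maximum. Three things follow.

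- Leaving out a baseline value that is already collected can waste precision the study can hardly spare, and leaves a chance pre-dose imbalance uncorrected.
- Two gene analyses with no order of precedence let a cell-level p-value be reported as a drug effect when it may reflect differences between a few patients.
- An analyst who follows the SAP alone would have no chemokine analysis to run and would run a different single-cell method from the protocol's.

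**Working it through.** **The plan's own figure.** The stated half-width of 0.77 SD for 9 patients is a one-sample t interval: t(0.975, 8)/√9 = 2.306/3 = 0.769. It reproduces. It describes one arm mean, so it neither supports nor weakens this point.

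**Patient numbers.** Protocol 3.1: 4 + 4 + 8 = 16, which is 12 vs 4 at 3:1. SAP Trial Design: 4 + 8 + 8 = 20, which is 15 vs 5. Protocol 6.1 maximum: 32, which is 24 vs 8 if all contribute.

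**Chemokines: what adjustment does.** The pre-post correlation r is not in the documents, so 0 to 0.7 is assumed. With N patients and G fitted groups, the variance of an ANCOVA arm contrast relative to the unadjusted one is (1 − r²) × (1 + 1/(N − G − 2)). Setting this to 1 gives the break-even r = 1/√(N − G − 1).

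| Model | r = 0 | r = 0.3 | r = 0.5 | r = 0.7 | Break-even r |
|---|---|---|---|---|---|
| Pooled, 12 vs 4 (G = 2) | 1.083 | 0.986 | 0.812 | 0.552 | 0.28 |
| Pooled, 15 vs 5 | 1.062 | 0.967 | 0.797 | 0.542 | 0.24 |
| Pooled, 24 vs 8 | 1.036 | 0.943 | 0.777 | 0.528 | 0.19 |
| Joint four-arm, N = 16 (G = 4) | 1.100 | 1.001 | 0.825 | 0.561 | 0.30 |
| Separate fit, 3 vs 4 (N = 7, G = 2) | 1.333 | 1.213 | 1.000 | 0.680 | 0.50 |

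Simulation of the pooled rows (40,000 trials per setting) agrees to within 0.01, with test size 0.047 to 0.051 for both methods. Simulated power for an assumed 1 SD effect at 12 vs 4 is 37% unadjusted, and 34%, 37%, 43% and 58% adjusted at r = 0, 0.3, 0.5 and 0.7. At 24 vs 8 it is 66% unadjusted, and 64%, 68%, 76% and 90% adjusted.

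The chance pre-dose imbalance at 12 vs 4 has SD √(1/12 + 1/4) = 0.577. An unadjusted contrast therefore typically shifts by r × 0.577 = 0.17, 0.29 and 0.40 SD at r = 0.3, 0.5 and 0.7.

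**Genes: why precedence matters.** Suppose the cell were the unit. With m cells per patient and intraclass correlation ICC, the design effect is 1 + (m − 1) × ICC, and a nominal two-sided 0.05 test rejects under the null with probability 2 × [1 − Φ(1.96/√design effect)]. At an assumed m = 100:

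- ICC 0.01: design effect 1.99, rejection 0.165
- ICC 0.05: design effect 5.95, rejection 0.422
- ICC 0.10: design effect 10.9, rejection 0.553

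Mann-Whitney simulations (3,000 trials) give 0.159, 0.393 and 0.547 at 12 vs 4, and much the same at the other two sizes. A t-test on patient means gives 0.044 to 0.057.

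**The case against.** **A patient-level gene analysis is already planned.** That is correct, and it limits the point to one missing sentence on precedence. A reader might infer that this trial's gene results will carry a 16 to 55% false-positive rate. The documents do not support that: they do not say the Scanpy comparison treats cells as independent, nor that arm statements will rest on it.

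**The stakes are disclaimed.** The synopsis, Protocol 10.1 and SAP Power Considerations all do so. This stands, and it sets the level of the consequence. It does not tell an analyst which analysis to run or report, and arm comparisons are planned all the same.

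**ANCOVA is a preference.** Its gain depends on a correlation nobody has stated, and the flow-cytometry ANCOVA is itself only exploratory. Below r of about 0.3 at 16 patients there is no precision gain. Comparing arms at the pre-dose time point would reveal an imbalance, but would not correct the post-dose contrast for it.

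**The pooled figures flatter it.** The study is dose-ranging, and the second BAL falls at different times across cohorts. For separate dose-level fits at 3 vs 4 the cost at r = 0 is 33%, not 8%. This stands and shapes the fix: a joint model costs about 10%.

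**The gene fix has no pre-dose term although BAL is taken before dosing.** True. The fix keeps the protocol's comparison by time point for genes and settles only which level governs.

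**Conclusion.** The point holds as a matter of method and document alignment. The chemokine comparison leaves out a baseline that is already collected, the SAP has no chemokine analysis and a different single-cell method, and the gene plan gives no precedence between its two levels.

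The size rests on assumed correlations, cell numbers and intraclass correlations. At 16 patients, adjustment costs 8 to 10% in variance if pre-dose and post-dose levels are unrelated, breaks even at r of about 0.28 to 0.30, and saves 17 to 19% at 0.5 and 44 to 45% at 0.7.

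Three stronger readings are tempting and unsupported:

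- *The primary result is invalid.* The SAP's primary endpoint is the combined CD4, CD8 and monocyte proportion, summarised with confidence intervals. The unadjusted chemokine test also keeps its size.
- *Dosing decisions hang on these p-values.* Escalation is decided "after the review of safety events in Cohorts 1 and 2".
- *Chemokines will go unanalysed.* The protocol plans the comparison; it is the SAP that omits it.

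The statements about the SAP rest on its text from the Introduction onward.

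**What to change.** 1. **Chemokines.** Analyse each by one ANCOVA of log post-dose level on arm and log pre-dose level. Fit placebo and the dose cohorts jointly, or pooled Auxora against placebo. Do not use separate two-arm fits.
2. **Genes.** Name the planned per-subject DESeq2 analysis as the only basis for Auxora-versus-placebo statements. Run it on counts summed per patient and cluster at each time point, rather than on averaged expression, because DESeq2 models counts. Keep cell-level Scanpy tests for cluster markers.
3. **SAP.** Add the chemokine outcome and analysis, the arm contrast, and the protocol's single-cell method.
4. **Status of p-values.** State that the blanket two-sided 0.05 does not apply to the chemokine and gene families, and label their p-values nominal and exploratory, in line with SAP Power Considerations.

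The cost is wording in both documents and a little code, with no new samples or patients. The price is the small loss of precision for any chemokine whose two levels are nearly uncorrelated, and cell-level gene lists that can no longer support an arm statement. A patient without a usable pre-dose chemokine value would drop out of the model, so the SAP should say how that case is handled.

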Live, CD45+ non-granulocytes will be sorted into 2% BSA in PBS solution, followed by wash, counting and capture for single cell RNA-sequencing using 10x Genomics 5' V2 chemistry. Followed standard single cell RNA-sequencing library preparation and quality control, libraries will be pooled in equimolar concentration and sequenced on Illumina NovaSeq 6000 (or another compatible instrument) to the depth of ~30,000 reads per cell. After demultiplexing reads will be aligned to a hybrid genome containing human (GRCh38) and SARS-CoV-2 (NC_045512.2) reference genomes. Resulting cell-by-gene matrices from all samples will be normalized using sctransform algorithm and integrated using BBKNN or scVI/scANVI approach followed by Leiden clustering, identification of marker genes for each cluster and assigning cell type identity to clusters (for details see [Grant et al., 2021](#)). It will be assessed whether treatment with Auxora resulted in emergence of the new clusters/cell types/cell states and markers characterizing these newly emergent populations will be evaluated. For homologous cell types differential genes expression analysis will be performed between Auxora- and placebo-treated subjects, split by time-points. The impact of Auxora treatment on detection of SARS-CoV-2 positive and negative strand RNA in infected cells will be assessed. Differential gene expression will be performed on per-cluster level and using multilevel statistics (per-cluster and per subject level, to assess biological variability within the group).

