## **STATISTICAL PRINCIPLES**

### Level of significance

All analyses will assume a two-sided type I error rate of 0.05.

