## **STATISTICAL ANALYSES**

#### Pharmacodynamic Analysis

Primary analyses will leverage descriptive statistics to summarize the change in combined proportions of CD4, CD8, and monocytes in BAL fluid by dose arm. Point estimates and corresponding 95% confidence intervals will be reported. We will explore ANCOVA models to compare the difference in post-dose proportions by arm, adjusting for pre-dose levels. Normality assumptions will be assessed and in the event of violation of assumptions, transformations or nonparametric approaches will be considered. Subsequent pairwise comparisons of each dose arm to placebo arm will be assessed as appropriate. Similar methods will be employed for additional flow cytometry endpoints as described above.

Exploratory analyses may also consider unsupervised methods including hierarchical clustering to further identify and visualize patterns in flow cytometry data.

Following single-cell RNA-sequencing, variable genes will be identified using a likelihood-ratio test in DESeq2. K-means clustering will then be used with selected genes to identify homogenous clusters with unique gene expression.

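### Protocol 10.6 feeds per-subject averages of expression into DESeq2, a model for raw integer counts; summed counts should be specified instead

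*Protocol*

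**What the plan says.** Protocol 10.6 plans the arm comparison of gene expression as follows: "For homologous cell types differential genes expression analysis will be performed between Auxora- and placebo-treated subjects, split by time-points". It has two layers. One works per cluster in Scanpy. The other adds the subject level, "to assess biological variability within the group, using averaged RNA expression and DESeq2 framework". Sections 2.3, 8.13.7 and 10.2 repeat the plan for multilevel statistics without naming an input, so 10.6 is the only place that says what goes into DESeq2.

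The only processed data layer that the protocol describes is in 8.13.7, repeated in 10.6: "Resulting cell-by-gene matrices from all samples will be normalized using sctransform algorithm", followed by integration, clustering and cell labelling. Nothing says that raw counts are carried forward or summed per subject.

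The SAP (Pharmacodynamic Analysis) uses DESeq2 for a different step: "Following single-cell RNA-sequencing, variable genes will be identified using a likelihood-ratio test in DESeq2", before K-means clustering. It states no input and does not mention the per-subject arm comparison.

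Protocol 10.2 lists the sequencing analysis under the primary pharmacodynamic endpoint. The SAP's primary endpoint is the combined CD4, CD8 and monocyte proportion alone, and Protocol 10.1 says the study is not powered for inference on the sequencing data.

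**The concern.** DESeq2 is a negative binomial model for raw integer counts, and it takes each sample's precision from the size of those counts. An average over cells is not a count. It is generally non-integer, is below 1 for most genes, and no longer shows whether it came from 50 cells or 500. An analyst who follows 10.6 literally meets an error, then has to round or rescale without any rule in the plan.

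This is the only Auxora-placebo gene-expression comparison that the protocol describes as made at subject level, so it is the one that reflects variation between patients. With about four placebo patients there is little information to spare. The SAP's primary endpoint looks for a fall in CD4, CD8 and monocyte proportions, so the number of cells per subject in the clusters of interest may also differ by arm, which is when losing the cell number matters most.

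**Working it through.** **The plan's own figure.** The only design figure is the half-width of 0.77 SD with 9 patients per arm (Protocol 10.1; SAP, Power Considerations). It reproduces: t(0.975, 8 df)/√9 = 2.306/3 = 0.769. It concerns a mean of a continuous endpoint. No figure is given for the DESeq2 analysis.

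**Inputs from the documents.** Two-sided 0.05 ("All analyses will assume a two-sided type I error rate of 0.05"). Allocation is 3:1 in cohorts of 4, 4 and 8 (for Cohort 3, "the next 8 patients will be enrolled in Cohort 3 and randomized 3:1 to Auxora or Placebo"), giving 3 + 3 + 6 = 12 Auxora and 1 + 1 + 2 = 4 placebo. The SAP's Cohort 2 of 8 would give 15 and 5. Sequencing is "to the depth of ~30,000 reads per cell".

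**Assumptions not in the documents.** 50 to 499 cells per subject and cluster; between-subject dispersion φ = 0.3; mean count per cell μ from 0.05 to 10; true effect none or 3-fold; Auxora doses pooled.

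**Step 1: variance.** A subject's mean over m cells has variance μ/m + φμ². A negative binomial model fitted to that mean assumes μ + φμ². The model standard error (SE) is therefore too large by √[(μ + φμ²)/(μ/m + φμ²)].

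- μ = 0.05, m = 50: √(0.05075/0.00175) = 5.4; m = 500: √(0.05075/0.00085) = 7.7
- μ = 1, m = 50: √(1.3/0.32) = 2.0; m = 500: √(1.3/0.302) = 2.1
- μ = 5, m = 50: √(12.5/7.6) = 1.3; m = 500: √(12.5/7.51) = 1.3

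**Step 2: simulation.** Negative binomial regression with a Wald test, Cox-Reid adjusted dispersion and no dispersion shrinkage; 1,500 runs per setting. It resembles the core of DESeq2 but is not DESeq2. Unrounded averages contained a non-integer value in 100% of runs. With averages rounded to integers, against raw sums with cell number as offset:

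| Mean count per cell | Rounded: one arm all zero | Rounded: model SE / empirical SD | Type I error, rounded vs summed | 3-fold effect detected, rounded vs summed |
|---|---|---|---|---|
| 0.05 | 100% | – | – vs 9.1% | – vs 87.1% |
| 0.2 | 94–98% | not meaningful | 0% vs 8.9% | 0% vs 89.9% |
| 1 | 0.1% | 1.44–1.56 | 0.1% vs 9.3% | 57.3% vs 92.3% |
| 3 | 0% | 1.10–1.18 | 3.3% vs 8.5% | 90.5% vs 91.0% |
| 10 | 0% | 0.95–0.99 | 7.6% vs 9.5% | 93.5% vs 91.9% |

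With sums the SE ratio is 0.87 to 0.92 throughout. The summed-count test is itself somewhat liberal here, a small-sample Wald excess, so part of the gap in detection reflects unequal type I error. It does not explain the genes lost to zeros.

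**Step 3: are such genes typical?** 30,000 reads over an assumed 20,000 genes is 1.5 reads per gene per cell on average, an upper bound on distinct molecules (UMIs). If gene means are log-normal, the share below 0.5, which rounds to zero, is Φ[ln(0.5/mean)/σ + σ/2].

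- 10,000 UMIs per cell, 12,000 genes (mean 0.833), σ = 1.5: Φ(0.41) = 66%
- 2,000 UMIs per cell, 18,000 genes (mean 0.111), σ = 2.5: Φ(1.85) = 97%

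**Step 4: lost cell numbers.** On the log scale a subject's value has variance of about 1/(mμ) + φ.

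- μ = 0.05: 0.4 + 0.3 = 0.70 with 50 cells; 0.04 + 0.3 = 0.34 with 500
- μ = 1: 0.32 and 0.302
- μ = 10: 0.302 and 0.3002

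Equal weighting therefore matters at low expression and hardly at all at high expression.

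**The case against.** The text at issue is one parenthesis, and averaging may be loose wording for the usual summing of counts per subject. That is possible, but nothing in either document says so, and the sentence as it stands names an unsuitable input.

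The plan mentions neither rounding nor rescaling; both are supplied here to make the model run. That stands, so the simulated sizes show what could follow and do not describe a planned step. A rejected input would also be noticed and corrected at the desk, with no patient or sample lost.

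Four stronger readings are tempting but unsupported:

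- *Normalised sctransform values, possibly negative, go into DESeq2.* Protocol 10.6 links sctransform to integration and clustering; it does not name the layer that is averaged.
- *The SAP repeats the error.* It names DESeq2 only for choosing variable genes and mentions no averaging. What it lacks is the per-subject comparison and its input.
- *The primary result is compromised.* The SAP's primary endpoint is a flow-cytometry proportion, the sequencing analysis is declared unpowered, and dose escalation rests on safety events.
- *Power collapses generally.* The loss from equal weighting depends strongly on the assumed direction of effect, spread of cell numbers and scaling factor, and nearly vanishes at 1 count per cell. No single power figure for it is defensible.

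**Conclusion.** The point holds as a should-fix. Protocol 10.6 states an input that DESeq2 is not built for, and no other passage corrects it. The input is either rejected or, once rounded or rescaled, loses low-expression genes or discards the cell number behind each subject's value. The error is mainly conservative: missed signal in genes with low or moderate expression, severe at or below about 0.2 counts per cell under rounding, material at 1, slight at 3 and negligible at 10. It would be wrong to infer that every gene's error bars are badly off.

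These sizes depend on the assumed cell numbers, dispersion, gene-expression distribution and rounding, and on a model without DESeq2's shrinkage. The mismatch between an average and a count model depends on none of them. The SAP's primary endpoint is unaffected; the importance comes from Protocol 10.2, which places sequencing under the primary pharmacodynamic endpoint.

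**What to change.** In Protocol 10.6, replace the reference to averages with: raw UMI counts summed over cells per subject, cluster and time point (pseudobulk), used as the DESeq2 input. Say that the sctransform, BBKNN and scVI/scANVI output serves only clustering and cell labelling. A stated minimum number of cells per subject and cluster would be a sensible addition.

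In the SAP (Pharmacodynamic Analysis), add the per-subject Auxora-placebo comparison with the same input, and state the input for the variable-gene step.

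The cost is a sentence or two in each document, with the same data and software and no further patients. The SAP's Technical Details already provide for documented changes.
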